11.3.5 Other Data

Other data collected at Screening and/or Admission will be listed by sequence and subject. These data are as follows:

- COT urine test
- Urine pregnancy test
- · Chest x-ray
- Urine drug screen
- Serology
- · Alcohol breath test
- · Prior medication
- · Product Test and Demonstration
- · Identification of NRT gum brand
- Willingness to use THS 2.2 and NRT gum products

Willingess and ability to use the products will also be summarized.

The data will be presented in the below outputs:

TFL number	Title	
TABLES		
15.2.1.1	Summary of Subject Disposition - Screened Population	
LISTINGS		
15.3.1.5	Listing of Product Test Willingness to Use the Product, Willingness to Quit Smoking, Readiness to Accept Smoking Interruption – Safety	
	Population – Salety	
15.3.1.6	Listing of Safety Laboratory Entry Criteria – Safety Population	
15.3.6.3	Listing of Prior and Concomitant Medication – Safety Population	

11.4 Measurements of Product Compliance

Levels of CO in exhaled breath will be measured to evaluate the exposure to CO (see Section 11.6.2.2.1 "Exhaled CO and COHb"), and to monitor compliance during the following study days (see Section 6.3.3 "Compliance to Product Allocation"):

- Wash-out on Day 0 and Day 2
- Single use Day 1 and Day 3 for subjects exposed to NRT gum.

CO data will be listed and summarized by sequence for all study days and timepoints as continuous variable and with the categorization \leq 10 ppm and \geq 10 ppm.

Values above 10 ppm will be highlighted in listings and be considered as non compliance if such values are observed prior to first product use on the single use days for all exposures and throughout the single use days for NRT gum exposure. During the washout days values above 10 ppm will be considered non-compliance on Day 2, but will be expected on Day 0 because smoking is ad libitum during Day -1. CO data leading to

Statistical Analysis Plan Final v 2.0 / 07 April 2014 Confidential
Page 42 of 73

exclusion of subjects from the analysis will be evaluated during the pre-analysis blind data review.

Number and percentage of subjects considered as non compliant during the study will be tabulated by sequence and study days for the Randomized population

The data will be presented in the below outputs:

TFL number	Title
TABLES	
15.2.4.10.1	Descriptive Statistics of Exhaled CO (ppm) During Single Use
	Continuous Measurements- PK Population
15.2.4.10.1.1	Descriptive Statistics of Exhaled CO (ppm) During Single Use by Sex -
	PK Population
15.2.4.10.1.2	Descriptive Statistics of Exhaled CO (ppm) During Single Use by
	Nicotine Level – PK Population
15.2.4.10.2	Descriptive Statistics of Exhaled CO (ppm) During Single Use
	Categorical Measurements- PK Population
15.2.4.11.1	Descriptive Statistics of Exhaled CO (ppm) During Days -1, 0, 2 and 4
	Continuous Measurements- PK Population
15.2.4.11.1.1	Descriptive Statistics of Exhaled CO (ppm) During Days -1, 0, 2 and 4
	by Sex – PK Population
15.2.4.11.1.2	Descriptive Statistics of Exhaled CO (ppm) During Days -1, 0, 2 and 4
	by Nicotine Level – PK Population
15.2.4.11.2	Descriptive Statistics of Exhaled CO (ppm) During Days -1, 0, 2 and 4
	Categorical Measurements- PK Population
15.2.5.1	Descriptive Statistics of Compliance-Randomized Population
LISTINGS	
15.3.3.5	Listing of Exhaled Breath CO (ppm) and Measurement Times - Safety
	Population

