6.2.2 Investigational Period (Day 0 to Day 3)

During the first washout, each subject will maintain nicotine abstinence from Day -1 at 11:00 PM to the time of single use of his/her allocated product at Day 1. At Day 1, after the single use of the product, subjects will maintain nicotine abstinence for the rest of the day. During the second washout on Day 2, subjects will maintain nicotine abstinence until the time of single use of subject's allocated product at Day 3. Subjects will not be allowed to smoke or use any other nicotine/tobacco-containing products other than the products/regimen they are allocated to.

Time point of first product use during study day (T_0) will be defined as start of the single product use at the single use days. The start time of the use of each product has to be documented on single use days (Day 1 and Day 3). The start of product use for THS 2.2 is defined as the time of the first puff. The start time for CC corresponds to the lighting of the CC, and the start time of the NRT gum is the time of the NRT gum intake. The 30 seconds it takes to pre-heat the Holder will not be taken into account. The subject must not take a puff of the Tobacco Stick during the pre-heating time.

Philip Morris Products S.A.	Clinical Study Protocol	Confidential
ZRHR-PK-02-JP	Final 1.0 / 21 June 2013	Page 45 of 122

For NRT gum, the start time and the stop time will be documented in appropriate log.

The start of the first product use can be different for each subject both days of product use; however, it must be in the window of 6:00 AM to 9:00 AM.

Single use of products (Day 1 and Day 3):

On Day 1 and Day 3, subjects will use the product they are randomized to only once in the morning between 6:00 AM to 9:00 AM, and will abstain from the product or other nicotine/tobacco-containing items for the rest of the day, i.e., subjects in the THS 2.2 arm will use one Tobacco Stick, subjects in the CC arm will smoke one CC, and subjects in the NRT gum arm will chew slowly the 2 mg NRT gum for 35±5minutes while spacing each chew (leading to an administered dose of 1 mg nicotine/product use as per label

	Sequence 1	Sequence 2	Sequence 3	Sequence 4
Day 1	THS 2.2	CC	THS 2.2	NRT gum
Day 3	CC	THS 2.2	NRT gum	THS 2.2

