6.5.4 Compliance to Investigational Products

Compliance for all arms will be ensured by strict distribution of the products (product by product) and collection of used Tobacco Sticks, the CC butts and the NRT gum after use will be documented in appropriate logs.

Confidentiality statement: Data and information contained in this document are considered to constitute trade secrets and confidential commercial information, and the legal protections provided to such trade secrets and confidential information are hereby claimed under the provisions of applicable law. No part of this document may be publicly disclosed without the written consent of Philip Morris Products S.A.

Philip Morris Products S.A.	Clinical Study Protocol	Confidential
ZRHR-PK-02-JP	Final 1.0 / 21 June 2013	Page 48 of 122

In addition, for subjects using NRT gum, the compliance will be chemically verified using exhaled CO breath. The cut-off point for the CO breath test value to distinguish tobacco use vs. no tobacco use will be 10 ppm (Benowitz et al., 2002).

Furthermore, the CO breath test will be considered as one of the measures of compliance during the wash-out days in all subjects.

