7.5.1 Biomarkers of Exposure

7.5.1.1 Biomarkers of Exposure to CO and COHb

Carboxyhemoglobin measured in blood and exhaled CO will be investigated as a measure of exposure to CO. The CO breath test will also serve as a measure of compliance in subjects using NRT gum as well as on the wash-out days in all subjects.

CO Breath Test

CO in exhaled breath will be measured using the Smokerlyzer[®] device such as Micro+TM Smokerlyzer[®] deviceor similar. The test will be performed for all subjects including the subjects using the NRT gum.

A CO breath test will be conducted once on Day -1 and Day 4:

On Day 0, Day 1, Day 2, and Day 3, four CO breath tests will be done per day. On Day 1 and Day 3, the first test per day will be performed within 15 minutes prior to T_0 . The three other tests will be conducted as described in section 9. On the wash-out days (Day 0 and Day 2), the first test will be conducted between 8:00 AM-9:30 AM the three other tests will be conducted as described in section 9.

Carboxyhemoglobin

Tests for COHb measurement will be performed at a local laboratory.

Blood samples will be taken as follows at Day 1 and Day 3:

A total of 5 blood samples will be taken. The first sample will be taken within 15 minutes prior to using the first product (T_0). Thereafter, the sampling times in relation to T_0 are at 15 minutes, 60 minutes, 4 hours and 12 hours post- T_0 .

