6.1.1 Timing of Confinement Period

The 6 day confinement period consists of:

- The Admission Day from admission on site until 06:30 AM on Day 0.
- The first washout period: from 06:30 AM on Day 0 until the time of first product use (T₀) in the time window 6:00 AM-9:00 AM of Day 1.
- The first product exposure period (1 day): starting from T₀ on Day 1, ending 24 hours after T₀.
- The second washout period: from the end of the first product exposure (24 hours after T₀ on Day 1) on Day 2 until the time of product use in the time window 6:00 AM-9:00 AM on Day 3.
- The second product exposure period (1 day): starting from T₀ on Day 3, ending 24 hours after T₀.
- The discharge procedures from 24 hours after T₀ of the second product use until the time of discharge on Day 4.

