6.3.3 Compliance to Product Allocation

Compliance will be ensured by strict distribution of the products (product by product) and collection of used Tobacco Sticks, the CC butts and the NRT gum after use. This information will be documented in appropriate logs.

In addition, in subjects using NRT gum, the compliance will be chemically verified using exhaled CO breath. The cut-off point for the CO breath test value to distinguish tobacco use vs. no tobacco use will be 10 ppm (Bennowitz et al, 2002).

Furthermore, the CO breath test will be considered as a measure of compliance during the wash-out days for all subjects.

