11.6.2.1.2 THS 2.2 vs NRT gum

The following analyses will be conducted in only Group-2 PK population:

The secondary analysis of C_{max} , $AUC_{(0-last)}$, $AUC_{(0-\infty)}$, $AUC_{(0-t')}$ and $t_{1/2}$ parameters will be performed parameters using the same ANOVA model as used for the primary analysis. (Section 11.6.1 "Primary Analyses").

Only subjects in the Group-2 PK population who provide evaluable data for both the THS 2.2 and CC products will be included in the analyses.

The analysis of C_{max} and AUC_(0-last) will test if the lower bound of the 95% CI for the ratio (THS 2.2 : NRT gum) is > 1.0 at the 0.025 level of significance in order to determine if the rate and the amount of nicotine absorbed of the THS 2.2 is higher relative to NRT gum. This approach will be used to test the following hypothesis for both C_{max} and $AUC_{(0-last)}$ parameters:

$$H_0$$
: $X_{THS} / X_{NRT} = 1.0$
 H_A : $X_{THS} / X_{NRT} > 1.0$

where X_{THS} and X_{NRT} are the adjusted geometrical means of THS 2.2 and NRT gum, respectively. H_0 is rejected with a type I error $\alpha = 0.025$ (one-sided test).

Statistical Analysis Plan Final v 2.0 / 07 April 2014 Confidential

Page 47 of 73

 To test if the time to the maximum nicotine concentration in THS 2.2 is shorter than in NRT gum the following hypothesis will be evaluated:

$$H_0$$
: X_{THS} - $X_{NRT} = 0$
 H_A : X_{THS} - $X_{NRT} < 0$

where X_{THS} and X_{NRT} are the median values of the THS 2.2 and NRT gum, respectively. t_{max} will be analysed on the original scale using the Wilcoxon Signed-Rank Test with a type I error $\alpha=0.025$ (one-sided test), as values are ordinal/discrete, and the assumption of normality may be questionable.

The analysis of t_{max} will be performed by calculating the difference for each subject (THS 2.2 – NRT gum) and obtaining the Hodges-Lehmann 95% CI estimates (**Hodges and Lehmann, 1963**). The median t_{max} for each product and the median difference between the products along with the 95% CI will be presented.

Supportive analysis will be performed as described in Section 11.6.3 "Supportive/Sensitivity Analysis".

The data will be presented in the below outputs:

Title
Analysis of Pharmacokinetic Parameters of Nicotine – Group-2 PK Population

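### Exhaled CO above 10 ppm after product use counts as non-compliance on gum days but not on THS 2.2 days, a one-directional detection gap in the Group-2 crossover

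*SAP*

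**What the plan says.** Protocol section 6.2.2 says that after the single use on Day 1 or Day 3 subjects "will abstain from the product or other nicotine/tobacco-containing items for the rest of the day". This holds for every product. Protocol section 7.5.1.1 adds: "On Day 0, Day 1, Day 2, and Day 3, four CO breath tests will be done per day". On product-use days the first test precedes T0. The other three fall at 12:00–1:30 PM, 4:00–5:30 PM and 8:00–9:30 PM (protocol Table 8, SAP Table 11).

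The threshold is the same in both documents: "The cut-off point for the CO breath test value to distinguish tobacco use vs. no tobacco use will be 10 ppm" (SAP section 6.3.3). Its use is not the same for all products. Protocol section 6.5.4 states that "for subjects using NRT gum, the compliance will be chemically verified using exhaled CO breath", and SAP section 11.4 carries this forward. Above 10 ppm is non-compliance "prior to first product use on the single use days for all exposures and throughout the single use days for NRT gum exposure". For wash-out days, "values above 10 ppm will be considered non-compliance on Day 2, but will be expected on Day 0". Exclusions based on CO are decided case by case at the blind data review. SAP Table 9 makes use of a non-assigned nicotine or tobacco product a major deviation and cites section 11.4 as an example of how it is identified.

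Group-2 (sequences 3 and 4 in SAP Table 1) tests Cmax and AUC(0-last) one-sided at 0.025 "in order to determine if the rate and the amount of nicotine absorbed of the THS 2.2 is higher relative to NRT gum". Only subjects evaluable on both products enter. The SAP says THS 2.2 and CC at that point; I read CC as gum.

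**The concern.** The two halves of one crossover are checked differently after use. AUC(0-last) is built on samples up to 24 hours, so a cigarette smoked later in the day adds to it. If it is smoked on a gum day, it lowers the THS 2.2:gum ratio, and the CO rule can lead to removal of that pair. If it is smoked on a THS 2.2 day, it raises the ratio, and the CO rule is silent. Selective removal of this kind can only move the ratio up, which is the direction of the alternative hypothesis.

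Neither document says why THS 2.2 days are left out. At stake are the estimate and the one-sided test of a secondary comparison, mainly for AUC(0-last). The first post-use breath test comes at 12:00 PM or later and T0 is no later than 9:00 AM, so CO bears on smoking hours after use more than on the early peak.

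**Working it through.** **1. What the CO rule covers after use in Group-2**

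| Sequence (n) | THS 2.2 day | Gum day |
|---|---|---|
| 3 (9) | Day 1: no post-use rule that day; a reading above 10 ppm on Day 2 counts, first test 8:00–9:30 AM | Day 3: all three post-use tests count |
| 4 (9) | Day 3: no post-use rule; the Day 4 test is not a compliance criterion | Day 1: all three post-use tests count, then Day 2 |

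The wash-out rule does not fill the Day 1 gap. SAP section 6.1.1 defines "The second washout period: from the end of the first product exposure (24 hours after" T0 on Day 1), so the hours after use belong to the exposure period. For sequence 4, half of Group-2, no CO criterion follows THS 2.2 use.

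**2. The plan's own figure**

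Inputs (SAP section 8): CV 21% for AUC(0-last), ratio 1.28, 90% power, one-sided 0.025.

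- SD of the log difference = √(2·ln(1 + 0.21²)) = 0.294.
- Noncentrality at n = 18 = ln(1.28)·√18 / 0.294 = 3.56.
- Power at 18 pairs is 91.9% (n − 1 df) or 91.7% (n − 2 df). The smallest n for 90% is 17 or 18 respectively.

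The planned 18 is reproduced, with at most one pair to spare.

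**3. Illustration of the tilt**

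Assumptions, none from the documents: k of the 18 subjects smoke covertly on the THS 2.2 day and another k on the gum day; each such day's AUC is multiplied by f; every affected gum day is flagged and the subject excluded. True ratio 1.00, paired t-test with n − 1 df, 200,000 simulated trials.

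Under the rule as written, 18 − k pairs remain, k of them inflated on the THS 2.2 side. The expected ratio is f^(k/(18 − k)). For f = 1.5 and k = 1 this is exp(0.4055/17) = 1.024.

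| f | k | As written: pairs | Ratio | One-sided error | Same rule on both days: pairs | Error | Power at 1.28 |
|---|---|---|---|---|---|---|---|
| 1.5 | 1 | 17 | 1.024 | 4.0% | 16 | 2.5% | 88% |
| 1.5 | 2 | 16 | 1.052 | 6.7% | 14 | 2.5% | 83% |
| 1.5 | 3 | 15 | 1.085 | 10.9% | 12 | 2.5% | 76% |
| 2.0 | 1 | 17 | 1.042 | 4.5% | 16 | 2.5% | 88% |
| 2.0 | 2 | 16 | 1.091 | 8.3% | 14 | 2.5% | 83% |
| 2.0 | 3 | 15 | 1.149 | 15.5% | 12 | 2.5% | 76% |

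With nobody excluded, the same contamination leaves the ratio at 1.00 and the error below 2.5%. The upward shift in these scenarios therefore comes from one-sided removal. With k = 0 there is no tilt.

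**4. Would the assigned stick itself trip the threshold?**

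Protocol Table 1 gives 1 mg CO per stick (ISO) or 0.6 mg (Health Canada Intense). Assume full uptake, 750 g haemoglobin binding 1.39 mL/g, and 6 ppm exhaled per 1% COHb.

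- 1 mg / 28.01 × 24.5 = 0.87 mL.
- 0.87 / (1.39 × 750) = 0.084 percentage points COHb.
- 0.084 × 6 = about 0.5 ppm.

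The conversion would have to be wrong by a factor of about 20 (10/0.5) for the stick alone to give 10 ppm. These conversion constants are assumptions, and machine yields are not measured uptake.

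**The case against.** The strongest reply is that CO is not the only control, and that the others apply to every product.

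- SAP section 7.1.4 sends any concentration inconsistent with the expected profile to review, and SAP section 6.3.2 has a PK expert flag anomalous data.
- SAP Table 9 makes covert smoking a major deviation on any exposure day, however it is found.
- Site staff dispense the products, and subjects have no free access to them (protocol section 6.6.1).
- A reading above 10 ppm on Day 2 counts for everyone.
- CO is tabulated at the 10 ppm cut for all days and time points, so THS 2.2-day values can be seen.

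All of this stands. A reader might infer that contamination on a THS 2.2 day cannot be found; the documents do not support that. But the anomaly review has no numerical criterion, and nicotine sampling after use thins out to 4, 6, 9, 12 and 24 hours. Supply control applies equally on gum days, where the plan still asks for a CO check.

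A second reply is that the threshold separates tobacco use from no tobacco use. Gum days are tobacco-free by design and THS 2.2 days are not. This may explain the protocol's choice, though neither document says so. The low CO yield and the interval of at least three hours before the first post-use test weaken it.

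Third, a single covert cigarette may not reach 10 ppm. If so, the gum rule does not fire either: there is no tilt, and a symmetric rule changes nothing. This also stands.

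Finally, protocol section 12.1.5 and SAP section 11.1.7 say that no claim rests on individual tests.

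**Conclusion.** The post-use CO criterion is asymmetric within Group-2, no reason is given, and any effect of removing flagged gum subjects runs toward the secondary hypothesis that THS 2.2 exceeds gum. The gap is clearest for sequence 4, where THS 2.2 is used on Day 3.

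The tilt needs covert smoking to occur, to exceed 10 ppm at a scheduled test on a gum day, and to lead to exclusion, which is not automatic. The documents give no rate or size for any of these, so the error rates of 4.0% to 15.5% above are illustrations under assumed contamination and not estimates for this trial.

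Two stronger inferences should be resisted. One is that the primary comparison is biased: in Group-1 neither THS 2.2 nor CC has a post-use CO criterion, so its two halves are treated alike. The other is to quote the shift from contaminating THS 2.2 days alone as the effect of the rule. One or two such days among 18 pairs would raise the ratio by f^(k/18), or 2.3% to 8.0% for f of 1.5 to 2, but that is the effect of the smoking. The rule contributes only through what it removes on the gum side.

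This is a gap worth closing before unblinding because the data are already collected. It is not evidence that the Group-2 result is wrong.

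**What to change.** In SAP section 11.4, treat exhaled CO above 10 ppm at any of the three post-T0 tests on a THS 2.2 single-use day as on a gum day: highlight it, count it as non-compliance, and send it to the same blinded data review.

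Apply any resulting exclusion to the nicotine PK analyses only, or present it as a Group-2 sensitivity analysis. Exhaled CO and COHb are endpoints analysed in the PK populations (SAP section 11.6.2.2.1). Removing THS 2.2 subjects because their CO was high would select on the outcome, so they should stay in those analyses. No change is needed for CC days.

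The cost is a sentence in the SAP, one programming flag and possibly some lost pairs. The plan has almost no slack: 90% power needs 17 or 18 pairs. In the illustration, power at a ratio of 1.28 falls to about 88% with one contaminated subject per product day and 83% with two. Part of that loss comes from gum exclusions that the present rule already allows. Keeping contaminated pairs is not free either: with one per product day and no exclusions, power is about 88% at 1.5-fold inflation and 79% at 2-fold.

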11.5 Extent of Exposure (Product Consumption)

Details of the product test prior to enrollment and of product use after randomization will be listed by sequence for the Safety population.

The number and percentage of subjects who smoked 1, 2, or 3 (categories of 0 and >3 will be included if applicable) THS Tobacco Stick at admission will be tabulated; together with the number and percentage of subjects who performed the NRT gum product trial, chewing for a period of 35±5min (categories of < 10min, ≥10min and <30min, >40min, or not performed will be added if applicable).

The number and percentage of subjects who smoked 0 or 1 (category >1 will be included if applicable) THS Tobacco Stick, or CC during single use days (Day 1 or Day 3) will be tabulated by sequence; together with the number and percentage of subjects who performed the single use day of the NRT gum chewed for a period of 35±5min

Statistical Analysis Plan Final v 2.0 / 07 April 2014 Confidential
Page 43 of 73

(categories of <10min, ≥10min and <30min, >40min, or not performed will be added if applicable).

The data will be presented in the below outputs:

TFL number	Title
TABLES	
15.2.2.1	Descriptive Statistics of Product Use - Safety Population
LISTINGS	
15.3.2.1	Listing of Product Usage – Safety Population
15.3.2.2	Listing of Cigarette Butt and Tobacco Stick Collection Data - Safety
	Population

11.6 Planned Statistical Analyses

11.6.1 Primary Analyses

The primary parameters C_{max} and $AUC_{(0-last)}$ will be listed and summarized as described in Section 11.1 "General Considerations" and subsections .

Only subjects in the Group-1 PK population who provide evaluable data for both the THS 2.2 and CC products will be included in the following analyses.

The primary analysis of C_{max} and AUC_(0-last) will be performed on the natural log-transformed parameters using an analysis of variance (ANOVA) model with terms for sequence, subject nested within sequence, period and product as fixed effect factors (Senn, 2002, FDA, 2001, CHMP, 2010, and CHMP Appendix IV, 2011).

Carry-over effect will not be tested, as it cannot be statistically distinguished from the interaction between product and period in a 2x2 crossover design.

The SAS code to be used is shown below:

```
Proc glm data=_data_;
Class subject sequence product period;
Model log_pk = sequence subject(sequence) period product;
Lsmean product / pdiff =control('CC') alpha=0.05 cl;
Run;
```

where "log pk" is the the natural log-transformed PK parameter being analyzed.

Supportive analysis will be performed as described in Section 11.6.3 "Supportive/Sensitivity Analysis".

LS means for each product will be back-transformed by exponentiation and will be tabulated together with the ratio (THS 2.2 : CC) and 95% CI.

Statistical Analysis Plan Final v 2.0 / 07 April 2014 Confidential

Page 44 of 73

The geometric CV will also be presented as $\text{CV}(\%) = 100\sqrt{(e^{\text{MSE}}-1)}$, where MSE is the mean square error of the fitted model residual.

The data will be presented in the below outputs:

TFL number	Title	
TABLES		
15.2.3.1	Analysis of Primary Pharmacokinetic Parameters of Nicotine -	
	Group-1 PK Population	
15.2.3.2	Analysis of Primary Pharmacokinetic Parameters of Nicotine by Sex	
	and Nicotine Level - Group-1 PK Population	
15.2.4.5	Descriptive Statistics of Pharmacokinetic Parameters of Nicotine – PK	
	Population	
15.2.4.5.1	Descriptive Statistics of Pharmacokinetic Parameters of Nicotine by	
	Sex – PK Population	
15.2.4.5.2	Descriptive Statistics of Pharmacokinetic Parameters of Nicotine by	
	Nicotine Level – PK Population	
FIGURES		
15.1.1.1	Primary Pharmacokinetic Parameters of Nicotine – Group-1 PK	
	Population	
LISTINGS		
15.3.3.1	Listing of Pharmacokinetic Parameters of Nicotine - Safety	
	Population	
15.3.2.6	Individual Efficacy Response Data – PK Population	

